## Research Design and Methods

The proposed study is a pilot RCT with multi-method longitudinal assessment (refer to **Figure 1** for an overview of study activities). The study has three primary aims: (1) to assess the feasibility of recruiting Veterans of color into an RCT of RBSTE, (2) to understand Veterans' views of the acceptability and appropriateness of intervention content and provider behavior and the feasibility of participation in a future RCT; and (3) to refine a holistic assessment strategy.

**Figure 1.** Schematic of study activities

Veterans who express interest in study participation will be contacted by study staff and provided with general information about the study. Those who continue to be interested will engage in the informed consent process in person or using remote procedures (e.g., VA Docusign), depending on personal and health considerations. Veterans who provide written consent will go on to complete the baseline assessment (refer to **Assessment approach**). Randomization will occur at the group level: once a cohort of 4-10 Veterans has enrolled and completed the baseline assessment, the cohort will be randomized by the study statistician. Although group randomization has disadvantages as compared to individual randomization (e.g., dependence among group members, lack of blinding of the final 1-2 groups), these can be managed and are outweighed in our experience by facilitating recruitment because groups can begin more quickly. Groups will meet in **weekly 90-minute sessions for 8 weeks**. Videoconferencing will be used to minimize barriers to participation, including transportation and public health concerns. The assessment battery will be repeated at the end of the group. Participants will be compensated \$50 for each assessment point for total compensation of \$100.

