**Assessment approach.** Because of the history of human rights violations and misconduct in medical and psychological research, many people of color mistrust research activities (Suite, La Bril, Prim, & Harrison-[name], 2007). This is an important reason to study the feasibility of the proposed data collection strategy and motivation to prioritize brevity of our assessment battery. A record of study participation will be gathered following CONSORT guidelines to quantify enrollment and retention. Assessments will be completed within 1 month prior to the beginning of group and within 1 month after the end of group. The sample will be characterized at the baseline assessment. Participant characteristics including age, gender, race/ethnicity, education, work status and financial and housing stability, will be gathered using a demographic questionnaire. Adherence to group will be quantified based on attendance at sessions and proportion of homework completed (**coded as none/partial/complete as judged by the therapist**).

**Recruitment feasibility.** Aim 1 of this study involves evaluating strategies for recruiting VOC for this type of study. *Enrollment rate*, defined as the number of contacts per enrollment, will be used to optimize the future approach to accrual. There is no target enrollment rate as many can be acceptable; this metric will serve to guide resource allocation. **Gathering information from Veterans and providers about reasons for declining participation or referral, however, will be important in determining the representativeness of the sample.** *Number of enrollments per month* will be viewed as successful if at least four individuals are enrolled per month as that level of recruitment represents a reasonable period (average 2-3 weeks) for a Veteran to wait for a group to begin. *Initiation rate* will be defined as the proportion of Veterans who initiate the intervention among all consented participants. This will inform recruitment strategies (i.e., which strategies lead to the highest proportion of treatment initiation) but also may help to identify areas of improvement in terms of connecting Veterans to the project. As these behaviors are recorded prior to the first session, we do not expect group differences.

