**Sample size.** As a feasibility study, the decision about sample size is not about establishing sufficient power to detect change in clinical outcomes but rather about demonstrating the viability of a future larger-scale study. The sample size was determined based on practical and quantitative considerations. We will aim for enrollment of 4 groups of each type of intervention, each with approximately 6 Veterans (average 6, range 4-10), leading to a total sample size of approximately 48 (24/cell) in the 15-month recruitment period. This rate of enrollment would demonstrate feasibility of a larger future study in that we would demonstrate that a steady flow of adequately sized intervention groups can be recruited. Given that this is a pilot and feasibility study, we are looking for clinical signal and feasibility rather than examining efficacy. All sample size analyses were performed using statistical package R. A two-sided type I error of 0.05 was assumed.

The sample size assessment was conducted for assessing the enrollment and completion rates. First, we assessed the precision of estimates based on projected sample size. We considered a range of target rate from 0.60 to 0.90 and estimated the width of the 95% exact binomial confidence interval for enrollment and completion rates for overall and for each intervention group (see **Table 1**).

**Table 1.** The width of 95% confidence intervals for enrollment and completion rates

Sample size	Estimated rate						
	0.60	0.65	0.70	0.75	0.80	0.85	0.90
48	0.267	0.261	0.251	0.239	0.222	0.201	0.174
24	0.365	0.357	0.345	0.329	0.308	0.282	0.249

From **Table 1**, if an estimated intervention initiation rate is 0.80, a sample size of 48 (total) and 24 (per intervention group) will produce a two-sided 95% confidence interval with a width of 0.222 and 0.308,

respectively. If an estimated intervention initiation rate is 0.90, the width of the 95% CI is reduced (becomes more precise, see **Table 1**) with the same sample size projected above.

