**Analyses.** The study has the goals of evaluating the viability and methodology of an RCT comparing two approaches to addressing race-based stress and trauma in VOC. Kraemer and colleagues (2006) have highlighted important limitations of effect sizes generated by pilot studies due to the large standard error. As a result, we will focus our analyses on examining feasibility and generating hypotheses for further examination. Descriptive statistics will be used to summarize the variables as well as to detect outliers, manage missing data and identify data entry errors. Wilcoxon rank sum test and Fisher's exact test will be used to assess the effectiveness of the randomization procedures by comparing baseline variables for participants between two intervention conditions. The primary analysis will be conducted for overall, and for each intervention group, respectively. The comparison of outcomes between intervention groups will be performed when it is necessary and appropriate. Multivariable analysis (logistic regression and linear regression) will be performed when it is appropriate. The associations between patient characteristics and other clinically important baseline variables with the study outcomes will also be assessed using univariate tests. Variables that are significantly associated with the study outcome (assessed by univariate test) or significantly different between study groups with  $p < 0.15$  will be included as potential covariates in the multivariable model. Backward elimination will be used to select the variables, and variables with  $p < 0.10$  will be retained in the final model. For the linear regression model, the outcome variable will be transformed if normal assumption of residuals is not satisfied.

**Aim 1:** *To examine the feasibility of recruiting VOC for an RCT comparing RBSTE and Present Centered Therapy (PCT) for management of stress related to discrimination experiences.*

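### Participant-level baseline significance tests are a poor check on whether cohort randomization worked; describe balance and audit the allocation record instead

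*Combined protocol and SAP*

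**What the plan says.** All references are to Research Design and Methods in the combined protocol and SAP.

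- **Purpose of the tests (Analyses).** Wilcoxon rank sum and Fisher's exact tests "will be used to assess the effectiveness of the randomization procedures by comparing baseline variables for participants between two intervention conditions". No threshold, variable list, multiplicity handling or standardized-difference criterion is given for this judgement. Descriptive statistics are planned, but for summarizing data and finding outliers, missing values and entry errors.
- **Second use (Analyses).** Variables that differ between study groups at p<0.15, or that are associated with the outcome, "will be included as potential covariates in the multivariable model". Backward elimination then keeps those with p<0.10.
- **Design (opening paragraphs).** "Randomization will occur at the group level". The statistician allocates a cohort of 4-10 once it has enrolled and completed baseline. Among the acknowledged drawbacks is "lack of blinding of the final 1-2 groups".
- **Size (Sample size).** "We will aim for enrollment of 4 groups of each type of intervention, each with approximately 6 Veterans", "leading to a total sample size of approximately 48 (24/cell) in the 15-month recruitment period". The same paragraph states "A two-sided type I error of 0.05 was assumed", but for the sample size work, not for the baseline comparison.

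**The concern.** A baseline significance test asks whether a difference is larger than chance would produce. When allocation is drawn at random after baseline data are in, chance is the only source of difference, so a small p-value does not indicate a faulty procedure. A large p-value is no better evidence in the other direction: with 24 per arm, a difference big enough to matter can be non-significant.

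The tests also compare participants although cohorts are randomized. If members of a cohort resemble one another at baseline, for instance because they were recruited in the same weeks or from the same clinic, the tests overstate the information available.

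At stake is what the pilot says about its own methods. The Analyses paragraph names the viability and methodology of an RCT as what the study evaluates, and a p-value is the only evidence on the randomization procedure that the plan specifies. The same comparisons also feed covariate selection for the between-group models.

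**Working it through.** **Inputs from the documents.** 24 per arm, 8 cohorts of about 6. Thresholds: 0.05 two-sided (Sample size) and 0.15 (the covariate rule in Analyses). Baseline variables: 7 demographics under Assessment approach ("age, gender, race/ethnicity, education, work status and financial and housing stability"), 6 questionnaires under Holistic evaluation counted as one score each, and the allostatic load index, giving 7 + 6 + 1 = 14. Adding the 10 individual markers gives 24. Testing subscales would raise the count.

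**Assumptions, because the documents give no values.** Correlation between baseline variables 0 to 0.5. Baseline intracluster correlation (ICC) 0 to 0.10.

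**1. The plan's own figures.** A two-sample t-test with 24 per arm, two-sided 0.05 and 80% power detects 0.826 SD (stated 0.83). Paired t-tests give 0.597 for n = 24 and 0.413 for n = 48 (stated 0.60 and 0.41). These reproduce.

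**2. Chance flags under sound randomization.** For k independent tests, P(at least one) = 1 − (1 − α)^k.

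- k = 14: 1 − 0.95^14 = 0.51; 1 − 0.85^14 = 0.90
- k = 24: 1 − 0.95^24 = 0.71; 1 − 0.85^24 = 0.98

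Fisher's test is conservative and the variables are correlated, so simulation (4,000 runs per setting, 4 versus 4 cohorts of 6, six binary variables and the rest continuous) gives lower values when there is no clustering:

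| Variables | Threshold | Independent formula | Simulated, ICC 0 | Simulated, ICC 0.05 |
|---|---|---|---|---|
| 14 | 0.05 | 51% | 38-43% | 51-58% |
| 14 | 0.15 | 90% | 80-86% | 87-92% |
| 24 | 0.05 | 71% | 51-65% | 65-82% |
| 24 | 0.15 | 98% | 90-97% | 96-99% |

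Ranges run over correlations of 0.5 to 0.

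**3. Imbalance that passes unflagged.** With the t-test standing in for Wilcoxon, the smallest observed standardized difference reaching significance is t × √(2/24), with 46 degrees of freedom.

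- At 0.05: 2.013 × 0.2887 = 0.58 SD
- At 0.15: 1.464 × 0.2887 = 0.42 SD

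For a binary variable, 12/24 versus 19/24, a gap of 29 percentage points, gives Fisher p = 0.069.

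**4. Wrong unit.** The design effect is 1 + (6 − 1) × ICC, which is 1.25 at ICC 0.05 and 1.5 at ICC 0.10. The approximate size of a nominal 0.05 test is 2{1 − Φ(1.96/√DE)}.

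- ICC 0.05: 1.96/1.118 = 1.753, size 0.080 (simulated Wilcoxon 0.077)
- ICC 0.10: 1.96/1.225 = 1.600, size 0.110 (simulated Wilcoxon 0.105)

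Moving the test to cohort level would not rescue it. If allocation is held at 4 and 4, there are only C(8,4) = 70 possible allocations, so the smallest two-sided permutation p is 2/70 = 0.029.

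**The case against.** Several points on the other side are fair.

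- **Likely false alarm.** A reader might infer that the pilot will probably report a false imbalance. The documents do not support that without more detail. At 0.05 with 14 variables and no clustering the chance is about even or less; it passes one half on the longer list, at the looser threshold or with clustering. The plan fixes neither the list nor the threshold.
- **Large imbalances missed.** A reader might also infer that large imbalances would escape. For continuous variables the exposure is to moderate ones: a true shift of 0.8 SD would be flagged about 77% of the time at 0.05, against 40% for 0.5 SD. The observed-difference limits in step 3 are the more relevant figures, since under random allocation there is no true shift to detect.
- **Partial cover from the covariate rule.** An observed 0.5 SD imbalance has t = 0.5/0.2887 = 1.73 and p of about 0.09, so the p<0.15 rule would nominate that variable. Variables associated with the outcome are nominated as well. This softens the effect on the models but leaves the stated purpose of the tests unrepaired.
- **Consequences.** Nothing says that a significant result would be reported as failed randomization or would change a later design. Balance is not among the success criteria, and the analyses are limited to feasibility and hypothesis generation.
- **Some diagnostic value.** Because the last one or two allocations are not blinded, a baseline comparison could hint at selective recruitment into those cohorts. With about eight randomized units the hint would be weak, and the allocation record addresses the risk directly.
- **Baseline clustering may be slight.** Groups have not met at baseline, so the ICC could be near zero, and the inflation in step 4 would then vanish.

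**Conclusion.** The point holds, as a minor one. The planned tests cannot support the conclusion assigned to them: under the described procedure significance reflects chance, and non-significance at this size does not show balance. Nothing elsewhere in the documents supplies another check.

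The false-flag range rests on the variable count taken from the documents (14 or 24), correlations of 0 to 0.5 and no clustering. The per-test inflation rests entirely on the assumed ICCs. The limits on unflagged imbalance use a t-test in place of Wilcoxon.

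It does not follow that the randomization itself is defective, or that the feasibility results would be invalid. The fault lies in how the procedure is to be judged, and in carrying the same comparisons into covariate selection.

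**What to change.** 1. Delete the baseline tests as a check on randomization, together with that stated purpose.
2. Tabulate baseline variables by arm with standardized differences, and show cohort-level means so that the eight randomized units are visible.
3. Judge the procedure from the allocation record: whether each draw was made after the cohort had closed and baseline was complete, whether each cohort was treated as allocated, and how many membership changes followed allocation. Report the final one or two unblinded cohorts separately.
4. Replace the p<0.15 between-group rule, which would otherwise lose its input, with a short list of covariates chosen in advance on prognostic grounds, such as the baseline value of the outcome where one is collected. The acceptability measures and the completion rates have no baseline value, so other prognostic variables would have to be named for them.

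The cost is minor SAP rewording and the loss of a familiar p-value column in the baseline table. The baseline data are already planned; the allocation log needs only to record dates and membership changes.

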**Acceptability, appropriateness and feasibility.** Relevant to aim 2, participant behavior is one important marker of participants' perceptions of the project and their ability to comply with research procedures. *Retention rate* will be defined as the percent of enrolled sample completing all assessment time points; at least 80% completion will be considered successful. *Per protocol completion rate* will be defined as the proportion of subjects who complete 6 or more sessions among those who initiate treatment; at least 90% completion will be considered successful. *Intent-to-treat completion rate* will be defined as the proportion of subjects who complete 6 or more sessions of intervention among all randomized subjects; at least 80% is the target. *Compliance with homework* will be assessed with a goal of at least 80% moderately or fully complete (refer to **Assessment approach**). In addition, Veterans will be directly queried about their experience using the *Acceptability of Intervention Measure (AIM)*, *Intervention Appropriateness Measure (IAM)*, and *Feasibility of Intervention Measure (FIM)*. The 5-item measures have strong content validity, test-retest reliability and sensitivity to change (Weiner et al., 2017). The psychotherapy version of the *Provider Rating Scales*, which were previously used to assess perceptions of VA mental health providers (Spoont et al., 2017), will be used to assess Veterans' perceptions of the group leader. Between-group differences on these measures would likely reflect the difference in content between the two groups.

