We will assess four outcome measures for enrollment and retention: 1) *enrollment rate* defined as the proportion of consented subjects among all screened and eligible patients; 2) *initiation rate* defined as the proportion of subjects who initiate the intervention among all consented subjects; 3) *per protocol completion rate* defined as the proportion of subjects who complete 5 or 6 sessions of intervention among those who start the intervention; 4) *intent-to-treat completion rate* defined as the proportion of subjects who complete 5 or 6 sessions of intervention among all randomized subjects. The 95% CI (based on normal approximation or exact binomial test when appropriate) will be estimated for all these rates for overall and by each intervention group. The rates for the RBSTE and PCT groups will be compared by Fisher's exact test. Multivariable analysis will be also performed to examine the difference in outcomes between intervention groups using logistic regression.

**Aim 2:** *To understand Veterans' views of the acceptability and appropriateness of treatment content, the feasibility of participation, and perceptions of provider behavior and attitudes.*

The AIM, IAM, FIM and Provider Rating Scales will be estimated by mean, SD and 95% CI. Intervention groups will be compared by Wilcoxon rank sum test. Multivariable analysis will be also performed to examine the difference in outcomes between intervention groups using linear regression.

**Aim 3:** *To optimize the strategy for holistic evaluation of intervention effects.*

As aforementioned, we will include a comprehensive list of cardiometabolic, neuroendocrine, and inflammatory markers that had been shown as reliable markers of AL in the literature to derive an AL index for each participant. We hypothesize that AL index at baseline will be associated with perceived discrimination as well as other psychosocial outcomes and that pre to post-intervention changes of AL index will differ between the two groups. We will perform regression analysis and variable selection using LASSO (Tibshirani 1996) to identify a smaller subset of the AL markers at baseline that show significant associations with psychosocial outcome measures. The effect size for pre and post change in AL markers will be estimated. This will inform future efficacy and effectiveness studies in potential reduction of a list of biomarkers to enhance feasibility, efficiency and reduce participant burden.

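### Covariate selection by a p<0.15 screen and backward elimination on about 48 people makes the Aim 2 adjusted arm interval modestly too narrow and often leaves noise variables in the final model

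*Combined protocol and SAP*

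**What the plan says.** The combined protocol and SAP, under Analyses, sets a two-stage rule. The entry criterion reads "Variables that are significantly associated with the study outcome (assessed by univariate test) or significantly different between study groups with" p<0.15. For the second stage, "Backward elimination will be used to select the variables", with p<0.10 needed to stay.

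The Aim 1 paragraph then states: "Multivariable analysis will be also performed to examine the difference in outcomes between intervention groups using logistic regression". The Aim 2 paragraph, which covers AIM, IAM, FIM and the Provider Rating Scales, states: "Multivariable analysis will be also performed to examine the difference in outcomes between intervention groups using linear regression". The general text qualifies this with "Multivariable analysis (logistic regression and linear regression) will be performed when it is appropriate", but gives no criterion for when that is.

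No candidate list, cap, fixed covariate or correction for selection is given. The nearest thing to a list is under Assessment approach: "Participant characteristics including age, gender, race/ethnicity, education, work status and financial and housing stability, will be gathered using a demographic questionnaire". Analyses also opens the pool to other clinically important baseline variables. The stated purpose is modest: "we will focus our analyses on examining feasibility and generating hypotheses for further examination".

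**The concern.** The same people decide which covariates enter, which survive, and how precise the final arm estimate appears. An ordinary regression interval treats the final model as if it had been chosen in advance. Backward elimination favours variables that happen to explain residual variation, so the reported residual variance tends to be too small. The choice of variables also varies from sample to sample, which adds real variability to the arm estimate that the reported standard error ignores.

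Separately, a 10% retention threshold applied to many candidates will usually let some noise through. Because this pilot is meant to generate hypotheses, a spurious predictor or an overstated precision could be carried into the design of the next trial.

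**Working it through.** **Inputs from the documents.** About 48 participants, 24 per arm, two-sided 5% (Sample size); entry p<0.15 and retention p<0.10 (Analyses); a retention target, "at least 80% completion will be considered successful" (Acceptability, appropriateness and feasibility), which gives 48 × 0.80 = 38.4, so n = 38 as a sensitivity case.

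**The plan's own figures.** The plan states none for covariate selection. Its detectable effects do reproduce from noncentral-t power at 80%: 0.826, 0.597 and 0.413, against the stated 0.83, 0.60 and 0.41.

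**Assumed inputs.**
- Number of candidates. Assessment approach names 7: age, gender, race/ethnicity, education, work status, financial stability and housing stability. One baseline score each for Brief PHI, DASS-21, TSDS, CDS, ethnic identity, ISI and the allostatic load index adds 7, making 14. Which would be screened is not stated, so 5 to 20 is shown as a range.
- Arm is always kept in the model (the plan does not say so).
- Participants are independent.

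**Noise retention, analytically.** If each of k independent null candidates survives with probability 0.10, P(at least one) = 1 − 0.9^k. This gives 52% for k = 7 and 77% for k = 14; 41% for k = 5 and 88% for k = 20.

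**Simulation of the rule, Aim 2 linear model.** There were 16,000 trials per main setting, with a true arm difference of zero. Candidates were screened by correlation with the outcome or Wilcoxon test against arm, then eliminated backward. The Monte Carlo standard error of coverage is about 0.2 points.

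| Result | 7 candidates | 14 candidates |
|---|---|---|
| Coverage of nominal 95% arm CI, n = 48 | 94.2% | 92.7% |
| Mean reported SE / actual SD, n = 48 | 0.282/0.296 = 0.95 | 0.276/0.304 = 0.91 |
| Coverage, n = 38 | 93.3% | 92.4% |
| At least one noise variable kept, n = 48 | 52% | 78% |
| 95% CI of a kept noise variable excludes zero | 100 − 44 = 56% | 100 − 39 = 61% |
| With two real predictors (R² 0.20, assumed): coverage | 94.1% | 92.5% |
| With two real predictors: at least one noise variable kept | about 35% | about 63% |

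Repeat simulations gave 93.9% to 94.2% (7 candidates) and 92.3% to 92.9% (14) at n = 48, with the SE 4% to 5% and 9% to 10% too small. For 14 candidates at n = 38 they ranged from 91.2% to 92.4%. Over 5 to 20 candidates, coverage at n = 48 runs from 94.0% to 91.9%. With candidates correlated 0.3 and five of them binary, it is 93.8% (7) and 93.3% (14).

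**Without selection.** With 7 or 14 candidates on file, using no covariates or two fixed ones gives coverage of 94.7% to 95.3%. The actual SD of the arm estimate, in outcome SDs, compares as follows:
- Unadjusted: √(2/24) = 0.289 in theory, 0.288 to 0.290 simulated.
- Two real predictors fixed in advance: 0.263 to 0.264.
- Two real predictors present, plan's selection rule: 0.272 (7) and 0.280 (14).
- Two useless covariates fixed: 0.295, and 0.295/0.288 = 1.02, a 2% loss.

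**Aim 1 logistic model.** With 10 non-completers (48 × 0.20 = 9.6), at least one noise variable is kept in 52% (7) and 77% (14) of trials. Arm CI coverage is 93.3% and 92.7% with selection, against 93% unadjusted, so no clear narrowing appears.

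**The case against.** The strongest reply is that little depends on these models. The plan itself warns against pilot effect sizes, makes the primary analysis overall and per arm, and already provides Fisher and Wilcoxon comparisons that involve no selection. With 7 candidates the loss is 95 − 94.2 = 0.8 points of coverage. The plan also does not explicitly promise an interval for the adjusted arm difference; it is implied by the regression comparison. All of this stands, and it keeps the point small.

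The noise-retention figures are for the all-null case. With 5 candidates of which three are real, the figure falls to 18%. That stands too.

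A reader might infer more than the documents support, in four ways.
- *That the Aim 1 arm interval is too narrow, or that the logistic model must go.* Coverage of the unadjusted logistic interval itself moves between about 92.5% and 97.5% with the number of non-completers, because the data are discrete; a different set-up gave 95% to 96% with selection at an 80% rate. With 5 non-completers, all fall in one arm with probability 2 × C(24,5)/C(48,5) = 85,008/1,712,304 = 5.0% before any covariate enters. The failed-fit rate beyond that depends heavily on set-up.
- *That reporting every association cures chance findings.* With independent null candidates, at least one 95% CI excludes zero in 1 − 0.95^7 = 30% or 1 − 0.95^14 = 51% of trials, against 32% and 56% under selection. The gain is that readers see how many were examined.
- *That most kept noise variables having intervals that exclude zero is a further defect.* It largely follows from keeping only p<0.10.
- *That the coverage figures describe this trial's actual intervals.* Cohorts are randomized and treated as groups; that dependence is a separate issue which these figures leave out.

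**Conclusion.** The concern holds in limited form and is worth considering rather than essential. Under 7 to 14 candidates, arm forced in and independent participants, the Aim 2 linear arm interval covers about 94% to 93% instead of 95% (about 92% with 14 candidates at n = 38), and its standard error is about 5% to 10% too small. If no candidate matters, the final model shows at least one noise variable in about 52% to 78% of trials; with two real predictors, about 35% to 63%. The direction does not change over 5 to 20 candidates, but the size does, and the documents do not fix the number.

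The feasibility conclusions are not touched. The enrollment rate, whose denominator is all screened eligible patients, the other descriptive rates, the Fisher and Wilcoxon comparisons and the success thresholds do not pass through the selection rule.

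**What to change.** Under Analyses, state that the p<0.15 screen and backward elimination are not used for comparisons between arms.

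In the Aim 2 paragraph, state that arm is always in the linear model, with one or two baseline covariates named before the first cohort is randomized and kept whatever their p-values.

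In the Aim 1 paragraph, if an adjusted logistic model is kept, apply the same no-selection rule and rely on the Fisher comparison when non-completers are few.

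Report every examined association between a characteristic and an outcome with its 95% CI, labelled exploratory and with the number examined. This improves transparency; it does not by itself reduce chance findings.

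The cost is wording only, with no new data. Chance imbalances in unnamed variables would be described, not adjusted for. If the named covariates prove unrelated to the outcome, the SD of the arm estimate rises about 2%. Using no covariates at all would also restore coverage, but would be less precise than the current plan if real predictors exist (SD about 0.29 against 0.27 to 0.28), so naming one or two is the better choice.

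### Treatment completion means at least six sessions where the 90% and 80% success levels are set, but five or six sessions where the rates are analysed

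*Combined protocol and SAP*

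**What the plan says.** Both definitions stand under Research Design and Methods of the combined protocol and SAP.

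- **Acceptability, appropriateness and feasibility.** The per-protocol completion rate is "the proportion of subjects who complete 6 or more sessions among those who initiate treatment; at least 90% completion will be considered successful". The intent-to-treat completion rate is the proportion of "subjects who complete 6 or more sessions of intervention among all randomized subjects; at least 80% is the target".
- **Analyses, Aim 1.** The per-protocol completion rate is "defined as the proportion of subjects who complete 5 or 6 sessions of intervention among those who start the intervention". The intent-to-treat completion rate is the "proportion of subjects who complete 5 or 6 sessions of intervention among all randomized subjects".
- **Programme length.** The opening text of Research Design and Methods sets "weekly 90-minute sessions for 8 weeks", which makes eight sessions.
- **Use of the rates.** Aim 1 continues: "The 95% CI (based on normal approximation or exact binomial test when appropriate) will be estimated for all these rates", overall and by arm. A Fisher's exact comparison of the arms and a logistic regression follow. Aim 1 restates no success level.

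**The concern.** The two sections use the same names and equivalent denominators (those who start; all randomized), so they describe the same two outcomes. The numerators differ. The 90% and 80% levels are attached only to the six-or-more rule, whereas the intervals, the Fisher's test and the regression are attached only to the five-or-six rule. An analyst who follows the Aim 1 text will report a rate for which no success level was set, and a reader will naturally compare it with 90% or 80%.

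In a feasibility trial these rates are main results: two of the four outcome measures listed for Aim 1. If the cut-off is settled only once attendance is known, it may be chosen, or seem to have been chosen, according to which version passes.

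**Working it through.** **1. The definitions side by side**

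| | Outcome section | Aim 1 analysis |
|---|---|---|
| Per-protocol denominator | those who initiate | those who start |
| Intent-to-treat denominator | all randomized | all randomized |
| Completer | 6, 7 or 8 sessions | 5 or 6 sessions |
| Success level | 90% and 80% | none stated |

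The Aim 1 wording can be read in two ways. As a minimum, it means at least five, one session more lenient than the outcome section. Literally, it means exactly five or six, which would class Veterans attending seven or eight sessions as non-completers. Neither reading equals six or more. The literal one is unlikely to be intended and carries no weight below.

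**2. Inputs for an illustration**

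From the documents: 8 sessions; planned n = 48; levels of 80% and 90%. Assumed, because the documents do not give them: per-session attendance p, within-person correlation rho, everyone randomized starts, and Veterans attend independently of one another (clustering within therapy groups is ignored).

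**3. Independent sessions**

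P(k sessions) = C(8,k) p^k (1 − p)^(8−k). At p = 0.80:

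- P(5) = 56 × 0.8^5 × 0.2^3 = 0.1468
- P(6) = 28 × 0.8^6 × 0.2^2 = 0.2936
- P(7) = 8 × 0.8^7 × 0.2 = 0.3355
- P(8) = 0.8^8 = 0.1678

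At least six: 0.2936 + 0.3355 + 0.1678 = 0.797. At least five: 0.797 + 0.147 = 0.944. Exactly five or six: 0.1468 + 0.2936 = 0.440.

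If some randomized Veterans never start, the intent-to-treat rate is lower. With 94.4% completion among starters, the 80% level needs 0.80 / 0.944 = 84.8% to start.

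**4. Correlated sessions**

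Veterans who miss one session tend to miss others, so a beta-binomial was used with n = 8, a = p(1/rho − 1) and b = (1 − p)(1/rho − 1).

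| Attendance | rho | At least 6 | At least 5 |
|---|---|---|---|
| 80% | 0 | 79.7% | 94.4% |
| 80% | 0.2 | 74.2% | 84.8% |
| 80% | 0.4 | 74.1% | 81.0% |
| 80% | 0.6 | 75.5% | 79.6% |
| 90% | 0 | 96.2% | 99.5% |
| 90% | 0.2 | 89.1% | 94.4% |
| 90% | 0.4 | 87.5% | 91.4% |
| 90% | 0.6 | 87.8% | 90.1% |

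At 80% attendance the gap is 14.7, 10.6, 6.9 and 4.1 points as rho rises; at rho = 0.6 neither cut-off reaches 80%. At 90% attendance with independent sessions, both cut-offs meet both levels. With correlation, they fall on opposite sides of the 90% level.

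**5. Chance of opposite verdicts with 48 Veterans**

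The levels need ceil(0.80 × 48) = 39 and ceil(0.90 × 48) = 44 completers. Each Veteran falls into one of three cells: six or more, exactly five, fewer than five. The multinomial then gives the probability that the count with six or more is below the required number while the count with five or more reaches it.

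| Level | Attendance | rho 0 | 0.2 | 0.4 | 0.6 |
|---|---|---|---|---|---|
| 80% | 70% | 54% | 10% | 5% | 3% |
| 80% | 80% | 52% | 64% | 40% | 24% |
| 80% | 90% | 0% | 3% | 6% | 5% |
| 90% | 80% | 85% | 13% | 3% | 2% |
| 90% | 90% | 4% | 48% | 33% | 19% |
| 90% | 95% | 0% | 8% | 12% | 8% |

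**The case against.** The strongest reply concerns importance. This is a pilot whose analyses are meant to examine feasibility and generate hypotheses. The levels are described as success marks and targets; no stop/go rule and no formal test is tied to them, and Aim 1 plans estimates with intervals and arm comparisons. Attendance is recorded ("Adherence to group will be quantified based on attendance at sessions and proportion of homework completed"), so either version can be computed later. All of that is true. It means that the harm is an ambiguous feasibility result, with no biased efficacy estimate and no safety consequence. It does not remove the contradiction, and being able to compute both versions later is what leaves the choice open.

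The size also depends on assumptions. The chance of opposite verdicts is large when attendance puts the rates near a level and negligible when it does not. That stands, and no single percentage above should be treated as established.

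The Sample size section states: "The sample size assessment was conducted for assessing the enrollment and completion rates". This shows that completion was central to planning, but the interval widths in Table 1 depend only on n and the assumed rate. The cut-off does not affect them, so there is no sample-size consequence.

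Two further defences are weak. The first is that separate measures were meant for Aims 1 and 2; but the names and denominators match, and neither cut-off is labelled secondary. The second is that this is a slip of the pen; but the five-or-six wording appears twice, and Preliminary Studies counts Veterans with more than four sessions in the existing groups, so a cut-off of five cannot be ruled out as the intended one.

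**Conclusion.** The concern holds. The text contradicts itself on two named outcomes that carry numerical success levels, and the rate specified for analysis is not the one to which those levels apply. This conclusion rests on the wording alone and needs no assumption. The practical effect cannot be fixed from the documents: in the illustrations the two minimum cut-offs give opposite verdicts with a chance of about 0% to 85%, depending on attendance and within-person correlation, with everyone assumed to start and group clustering ignored. The definitions must be reconciled before data are seen.

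**What to change.** Use one completer definition throughout. The direct route is to replace the five-or-six wording in both Aim 1 definitions with at least six of the eight sessions, matching the section that sets the 90% and 80% levels. This also makes clear that Veterans attending seven or eight sessions are completers and those attending five are not.

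If at least five is what the sponsor intends, change the outcome section instead and justify the 90% and 80% levels afresh for that cut-off.

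The first route costs two phrases. Neither route needs extra data, since session attendance is already collected, and neither changes the sample size or Table 1.
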